**LIST OF ABBREVIATIONS**

AE	Adverse Event/Adverse Experience
AUC	Area Under the Serum-Concentration Curve
C max	Maximum Serum Concentration
C ss	Steady State Concentrations
CFR	Code of Federal Regulations
CL	Clearance
CNS	Central Nervous System
CRF	Case Report Form
CRU	Clinical Research Unit
ECG	Electrocardiogram
FDA	Food and Drug Administration
GCP	Good Clinical Practice
HIPAA	Health Insurance Portability and Accountability Act
ICH	International Conference on Harmonisation
ICTS	Institute for Clinical and Translational Science
IRB	Institutional Review Board
ISM	Independent Safety Monitor
IV	Intravenous
K el	Elimination Rate Constant
MAI	Medically Accountable Investigator (i.e., licensed clinician)
NBP	Noninvasive Blood Pressure
PI	Principal Investigator
PK	Pharmacokinetics
PSI	Primary Skin Irritation
QA	Quality Assurance
QC	Quality Control
QM	Quality Management
QMP	Quality Management Plan
RIHSC	Research Involving Human Subjects Committee
RLD	Reference Listed Drug
SAE	Serious Adverse Event/Serious Adverse Experience
SpO 2	Oxygen Saturation
T max	Time of Maximum Serum Concentration
UI	University of Iowa
UICOP	University of Iowa College of Pharmacy
UIHC	University of Iowa Hospitals and Clinics
US	United States
V	Volume of Distribution

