### 2.2. Rationale

The rationale of this study is to determine the absolute bioavailability and pharmacokinetics of topical lidocaine through development of an appropriately controlled and well-characterized methodology to quantify the exposure of healthy adults to lidocaine during wear, so that the rate of drug release and delivery can be defined in a manner that can help the regulatory agency (FDA) in developing Guidances for Industry regarding the characterization of drug release and absorption kinetics to ensure the safety of individuals utilizing these types of products.

The project involves crossover pharmacokinetic (PK) studies using two lidocaine topical patch products made by different manufacturers, and IV injection of the corresponding drug (e.g. lidocaine hydrochloride). The IV data will be utilized to determine clearance (CL) of the drug from the systemic circulation. Different mathematical approaches including, but not limited to, deconvolution will then be utilized to determine the rate of drug delivery from the patch into the systemic circulation using PK parameters derived from non-compartmental and/or compartmental analyses of lidocaine serum concentrations measured using sensitive, validated bioanalytical methods. In order to compare the data obtained from this study to previously published data, a similar time course was selected for collecting the blood samples for serum analysis. As part of this study, appropriate methodologies will also be developed to precisely characterize the (residual) drug content in the selected products. Following the *in vivo* studies, residual drug content of the worn patches will be determined to calculate exposure from the patch (i.e. quantifying the amount of drug delivered *in vivo* over time based upon residual drug analysis data).

Since this will be a crossover study, all subjects will complete all three study arms. One of the patch systems will be applied first, followed by at least 48 hours of washout period. Then the IV injection will be administered followed by at least 48 hours of washout period. Last, the second patch system will be applied. Subjects will be assigned to one of two groups. Regardless of group, all subjects will receive the treatments in the same order of patch-IV-patch. In Group 1 the patch manufactured by Mylan will be applied first; in Group 2 the patch manufactured by Endo Pharmaceuticals will be applied first.

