The study has been designed to reduce these potential risks as follows. According to the FDA approved dosing, up to three patches may be applied once for up to 12 hours, in a 24 hour period. Thus, the proposed dosing regimen in this study is three patches, applied to the lower back. The skin will be carefully inspected prior to patch application and patches will not be applied to skin that is irritated or compromised in any way. The patches will be removed at the end of the approved 12-hour wear period. This dosing regimen will be used for both types of patches studied. The mean peak plasma concentrations obtained from this dosing regimen is expected to be approximately 0.13 µg/ml, which is ~1/10th of the concentration required for treatment of cardiac arrhythmias (0.4 ± 6.0 µg/mL are considered therapeutic for treatment of cardiac arrhythmias).

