#### 4. STUDY DESIGN

This is a three arm, open-label, crossover clinical pharmacokinetic (PK) study in 24 healthy human volunteers. The study will consist of 8 – 9 procedure days with a minimum 48 hour washout period between study arms. Two study arms are based on topical administration of lidocaine patches, and a third arm is based on IV administration. A study arm is defined as the entire administration and PK assessment period of either lidocaine topical patches or lidocaine hydrochloride injection.

The study products are:

- Lidoderm® patch 5% (Endo Pharmaceuticals)
- Lidocaine patch 5% (Mylan)
- Lidocaine hydrochloride 20 mg/1ml preservative free single dose vials

Each subject will be his/her own control and each subject will sign an Institutional Review Board (IRB) approved informed consent document explaining the purpose, nature, risks, benefits, and duration of the study. The study will be conducted in accordance with good clinical practice (GCP) guidelines and with the ethical principles originating in the Declaration of Helsinki.

The subject's skin in the area of application (skin of the lower back) will be relatively free of hair before patch application. Blood samples (approximately 5 mL each) will be drawn into vacutainer serum tubes. Blood samples will be obtained at the following time points (based on administration route):

- Within 60 minutes pre-patch application and then 1:00, 2:00, 3:00, 4:00, 5:00, 6:00, 8:00, 10:00, 12:00 (patch removal), 14:00, 24:00, 27:00, 30:00, 33:00, 36:00, 39:00, 48:00 hours post-patch wear. Total of 18 samples for each patch used.
- Within 60 minutes pre-IV infusion and then 2, 5, 10, 20, 30, 45, 60 min, then 2:00, 3:00, 4:00, 6:00, 8:00, and 10:00 hours post injection. Total of 14 samples.

The total volume to be drawn from the subjects for the entire duration of the study will be approximately 250 mL or 17 tablespoons.

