The half-life of topical lidocaine after patch removal is approximately 6 – 8 hours. Hence, 48 hours (i.e. ~5 to 6 half-lives) will be sufficient for >95% of lidocaine to be eliminated from the body after topical administration. The half-life after IV administration is approximately 1.5 – 2 hours. Ten hours of sampling will be sufficient for >95% of lidocaine to be eliminated from the body. Each subject will be enrolled to complete all study arms and procedure days. The study is open-label and not blinded because PK assessment is not subject to participant and/or observer bias. After each study arm is completed, the available safety data will be reviewed by an Independent Safety Monitor (ISM) to determine whether or not the subject will proceed to the next study arm.

A schedule of events is provided in **Appendix A**.

This study will be conducted in the CRU outpatient unit of the Institute for Clinical and Translational Science (ICTS) in the University of Iowa Hospitals and Clinics (UIHC). Conducting studies in this well-prepared research-oriented unit ensures that each subject is carefully observed throughout the study. If any adverse events occur, they can be properly documented and the subjects provided with the appropriate care. The CRU is a fully equipped research unit in UIHC, with inpatient and outpatient facilities, nursing staff on site and the MAI is available on- or offsite via the hospital pager system. The hospital code team is available to manage any unanticipated life-threatening emergency, and less urgent issues will be managed by the MAI.

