Finally, the lidocaine absorption rate will be calculated using steady state concentrations ( $C_{ss}$ ) and the clearance (CL) as predicted from the IV bolus data:

$$Absorption\ rate = C_{ss} \times CL$$

**Equation 4:** Determination of the absorption rate from lidocaine patches using the steady state concentrations and the clearance.

A detailed explanation of the statistics to be performed on the PK analysis is presented in **Section 10.4.**

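### Equation 4 takes the absorption rate as Css × CL, but the plan does not say which samples give Css, does not check steady state within the single 12 h wear, and does not say which rate is meant

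*Combined protocol and SAP*

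**What the plan says.** Section 10.2 introduces Equation 4 with "Finally, the lidocaine absorption rate will be calculated using steady state concentrations" and takes clearance from the IV arm. The caption of the equation reads "Determination of the absorption rate from lidocaine patches using the steady state concentrations and the clearance". The List of Abbreviations expands Css as "Steady State Concentrations" and adds nothing more. Css is not among the pharmacokinetic parameters listed in Sections 3.2 and 10.2. Section 10.2 sends the reader to Section 10.4 for statistical detail, and Section 10.4 mentions neither Css nor an absorption rate.

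On design, Section 2.3.1 states "The patches will be removed at the end of the approved 12-hour wear period". The later part of the sampling schedule in Section 4 runs "6:00, 8:00, 10:00, 12:00 (patch removal), 14:00, 24:00", so 12 h is the last sample on the patch. Section 4 also gives two half-lives: "The half-life of topical lidocaine after patch removal is approximately 6 – 8 hours" and "The half-life after IV administration is approximately 1.5 – 2 hours".

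Two other rate methods are planned. Section 2.2 says that "deconvolution will then be utilized to determine the rate of drug delivery from the patch into the systemic circulation", and Sections 3.1 and 10.2 name deconvolution again. Equation 3 divides the amount released (from residual drug) by the application time. No section says which serum-based estimate takes precedence.

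**The concern.** Css × CL equals the rate of input to the circulation only when the serum level has stopped changing. After a single 12 h application that is an assumption. The stated half-life is longer after patch removal than after IV dosing, which suggests that drug keeps entering from the skin. The level may therefore still be rising at 12 h.

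Two choices are left open. One is the level: the 12 h sample, a late-wear mean, or something else. The other is the rate it represents: the rate near the end of wear, or the average over wear. Two analysts could report different rates from the same data.

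Comparison with Equation 3 is also at stake. The study sets residual-drug and serum-based estimates side by side to learn which methods characterise delivery. The two formulas average over different things, so a gap between them could be read as incomplete absorption when it comes only from the definitions. The rate of delivery is the objective in the Protocol Summary, and absorption rates are the third objective in Section 3.1.

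**Working it through.** **Inputs from the plan.** Wear time 12 h; wear-time samples at 1, 2, 3, 4, 5, 6, 8, 10 and 12 h; half-life after removal 6–8 h; half-life after IV 1.5–2 h. No clearance value is given, so all results are ratios.

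**The plan's own figures.** Section 4 says that more than 95% is eliminated by 48 h (topical) and by 10 h (IV). With fraction eliminated = 1 − 2^(−t/half-life):
- Topical, 48 h: 98.4% (8 h half-life) to 99.6% (6 h).
- Topical, 36 h counted from removal: 95.6% to 98.4%.
- IV, 10 h: 96.9% (2 h) to 99.0% (1.5 h).

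These statements hold.

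**What the half-lives say about 12 h.** Let f(t) be the absorption rate into the circulation, y(t) = C(t) × CL, and ke = ln 2 / IV half-life. Then dy/dt = ke(f − y), so y equals f only when y is flat. Three assumed inputs were compared; h is the half-life after removal.

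1. *IV kinetics alone* (constant input, no skin delay): y(12)/plateau = 1 − 2^(−12/1.5) = 0.996 and 1 − 2^(−12/2) = 0.984. The 8 h values are 0.975 and 0.9375, so the rise from 8 to 12 h is only 2% to 5%.
2. *Depot* (constant release R0 into skin, first-order exit with half-life h): f(12)/R0 = 1 − 2^(−12/h). With ka = ln 2/h, y(12)/R0 = 1 − (ke·e^(−12ka) − ka·e^(−12ke))/(ke − ka).
3. *Diffusion slab* (fixed concentration at the outer face during wear, no flux there after removal, sink at the inner face, terminal half-life after removal set to h): relaxation on the patch is then 4 times faster than the decline after removal. To leading term, f(12)/steady flux = 1 − 2·2^(−4×12/h), which is 0.992 for h = 6 and 0.969 for h = 8.

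Depot example, h = 6 and IV half-life 1.5 h: ka = 0.1155, ke = 0.4621, and y(12)/R0 = 1 − (0.4621 × 0.25 − 0.1155 × 0.0039)/0.3466 = 0.668. The rate at 12 h is 0.750, giving 0.668/0.750 = 0.891. Mean absorption over wear is 1 − 0.750/(12 × 0.1155) = 0.459, giving 0.668/0.459 = 1.455.

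For the Equation 3 comparison, assume that all released drug is eventually absorbed. Then y(12)/(released/12 h) = [y(12)/wear mean] × share absorbed during wear. The share absorbed after removal is 0.541 and 0.622 (depot, h = 6 and 8) and 0.557 and 0.657 (slab). In the example, 1.455 × (1 − 0.541) = 0.668.

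| Model; h, IV half-life (h) | C12×CL / plateau | C12 / C8 | C12×CL / rate at 12 h | C12×CL / wear mean | C12 / mean(8, 10, 12 h) | C12×CL / (released/12 h) |
|---|---|---|---|---|---|---|
| Depot 6, 1.5 | 0.668 | 1.394 | 0.891 | 1.455 | 1.16 | 0.67 |
| Depot 6, 2 | 0.633 | 1.451 | 0.844 | 1.379 | 1.18 | 0.63 |
| Depot 8, 1.5 | 0.566 | 1.449 | 0.875 | 1.496 | 1.18 | 0.57 |
| Depot 8, 2 | 0.534 | 1.507 | 0.826 | 1.411 | 1.20 | 0.53 |
| Slab 6, 1.5 | 0.955 | 1.187 | 0.962 | 1.355 | 1.08 | 0.60 |
| Slab 6, 2 | 0.919 | 1.255 | 0.927 | 1.305 | 1.10 | 0.58 |
| Slab 8, 1.5 | 0.905 | 1.307 | 0.935 | 1.479 | 1.12 | 0.51 |
| Slab 8, 2 | 0.862 | 1.386 | 0.890 | 1.409 | 1.15 | 0.48 |

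In both skin models the peak falls at 12.8–15.0 h, after removal, so Cmax is not a wear-time level.

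**Could the data settle it?** Assume 10% CV per sample and 24 subjects. The 95% CI half-width of the geometric mean 8-to-12 h ratio is about 2.07 × √2 × 0.10/√24 = 0.06, or ±6% (sampling noise only). That helps to separate a 2–5% rise from a 19–51% rise.

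**The case against.** The strongest reply is that little hangs on Equation 4. Deconvolution, which needs no steady state, is already planned. Equation 4 comes last in Section 10.2, Css is not an outcome measure, and the primary analysis in Section 10.4 does not use it. All of that stands and limits the weight of the point.

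A reader might infer from the 6–8 h half-life that a plateau by 12 h is ruled out, at only 1 − 2^(−12/8) = 65% to 1 − 2^(−12/6) = 75% of it. The documents do not support this. That half-life describes the decline after removal, and those percentages assume the same half-life for the rise on the patch. In the slab model, with the same half-life after removal, the 12 h level is 86–96% of plateau. With IV kinetics alone it is above 98%.

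A reader might also infer that Equation 4 overstates absorption. The 30–50% excess arises only if the product is read as the average over wear, which Section 10.2 does not say. Against the rate at 12 h it is 4–17% low.

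Counting Cmax as a candidate for Css would widen the spread between choices, but Cmax is its own listed parameter and should not be counted.

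None of these replies supplies a definition of Css, a check on steady state, or an order of precedence among the rate estimates.

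**Conclusion.** The point holds as a minor one on a secondary analysis. A written formula depends on a steady state that the design neither ensures nor checks, and its main input has no operational definition.

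Across the three assumed inputs, the 12 h level could be anywhere from about 53% to over 99% of plateau, and the documents cannot choose among them. In the two skin models:
- Serum still rises 19–51% from 8 to 12 h.
- Replacing the 12 h level with the mean of the 8, 10 and 12 h levels changes the result 1.08- to 1.20-fold.
- The 12 h product is about 48–67% of the released amount divided by 12 h, even with complete absorption.

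These sizes depend on the models and on the stated half-lives applying to both patches. The need to define Css and to name the rate depends on neither. No primary result is affected.

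**What to change.** In Section 10.2:
- Name the planned deconvolution, against each subject's own IV profile, as the primary estimate of the absorption rate.
- Keep Equation 4 only as a supportive, approximate rate near the end of wear. State the wear-time level used (for example the 12 h sample; not Cmax), and apply it to all subjects and both patches.
- Report the geometric mean 8-to-12 h serum ratio with its 95% CI for each patch, so that readers can judge whether a plateau was reached.
- State that Equation 3 (release averaged over application time) and Equation 4 (apparent systemic input near the end of wear) are different rates, and that a gap between them is not in itself evidence of incomplete absorption.

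The cost is a little more analysis and some wording. No new samples, visits or data are needed: deconvolution uses the IV arm that Equation 4 already requires, and the 8 h and 12 h samples are already scheduled.

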### 10.3. Sample Size Consideration

A power analysis determined a sample size of 24 as sufficient for an alpha  $\leq .05$  to reject the null hypothesis and establish statistical significance. This analysis assumed a 22% within subject variability in the pharmacokinetic parameters,  $C_{Max}$  and  $AUC_{0-\infty}$ , with 80% power. The analysis also assumed that the test and reference formulation vary by 5% and a type-I error rate of 5%.

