## 6. STUDY PRODUCT

### 6.1. Study Product Description

#### 6.1.1. Lidoderm® Patch 5%

Lidoderm® patch 5% is a prescription product that delivers approximately  $3 \pm 2\%$  of the applied dose over a 12 hour wear time. At least 95% (665 mg) of lidocaine is expected to remain in the worn patch after removal.

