#### 6.1.3. Lidocaine Patch 5% (Mylan)

The Mylan lidocaine patch 5% is a prescription product that delivers approximately  $11 \pm 4\%$  of the applied dose over a 12 hour wear time. At least 82% (115 mg) of lidocaine is expected to remain in the worn patch after removal.

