#### 6.3.1. Lidoderm® Patch 5%

[figure not shown]
Active ingredient: lidocaine, 700 mg (50 mg per gram of adhesive). In addition to the active ingredient (lidocaine), the following inactive ingredients are present in the patch: dihydroxyaluminum aminoacetate, disodium edetate, gelatin, glycerin, kaolin, methylparaben, polyacrylic acid, polyvinyl alcohol, propylene glycol, propylparaben, sodium carboxymethylcellulose, sodium polyacrylate, D-sorbitol, tartaric acid, and urea. This is a hydrogel patch manufactured by Endo Pharmaceuticals.

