## 10. PHARMACOKINETICS AND STATISTICAL CONSIDERATIONS

### 10.1. Study Hypotheses

The main objective of this study is to determine the absolute bioavailability and PK parameters (e.g., AUC,  $C_{max}$ ,  $T_{max}$ , CL, V) of lidocaine in healthy adults after using lidocaine 5% patches manufactured by Endo Pharmaceuticals and Mylan. The secondary objective is to determine residual drug content in worn patches.

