### 10.4. Statistical Analysis Plan

Primary statistical analysis will be performed on the natural log transformed  $AUC_{0-t}$ ,  $AUC_{0-\infty}$  and  $C_{max}$  of lidocaine from the two treatments. The following will be obtained:

- A linear mixed effects model will be used to assess the effects of treatment, period, sequence, and subject within sequence on the natural log transformed  $AUC_{0-t}$ ,  $AUC_{0-\infty}$  and  $C_{max}$  of lidocaine. For this, the treatment, period, and sequence effect will be treated as fixed effects (assessed at a significance level of 0.05) while the subject within sequence will be treated as a random effect.
- Intra- and inter-individual variabilities will be obtained.
- The least squares mean estimates for the adjusted differences between treatment means (the log transformed  $AUC_{0-t}$ ,  $AUC_{0-\infty}$  and  $C_{max}$ ) and the standard error associated with these differences will be obtained.
- The 95% confidence intervals for absolute bioavailability of the lidocaine patches will be obtained.

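### The 80% power in section 10.3 does not belong to the patch comparison planned in section 10.4, which has about 12% power for the stated 5% difference at n=24

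*Combined protocol and SAP*

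**What the plan says.** Section 10.3 gives the only rationale for the sample size. It takes 22% within-subject variability in Cmax and AUC0-∞ and 80% power, and adds: "The analysis also assumed that the test and reference formulation vary by 5% and a type-I error rate of 5" percent. The stated purpose is "to reject the null hypothesis and establish statistical significance". The null, the sidedness and any margin are not given.

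Section 10.1 is headed Study Hypotheses but contains objectives only: "The main objective of this study is to determine the absolute bioavailability and PK parameters".

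Section 10.4 fits a linear mixed model to log AUC and log Cmax for two treatments that it does not name. In that model "the treatment, period, and sequence effect will be treated as fixed effects (assessed at a significance level of 0.05"). It also plans least squares mean differences with standard errors. The only interval it plans is this: "The 95% confidence intervals for absolute bioavailability of the lidocaine patches will be obtained". No section mentions equivalence limits, two one-sided tests, or a 90% confidence interval for a patch ratio.

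Sections 6.1 and 6.3 bear on the assumed 5%. Lidoderm is said to deliver 3 ± 2% "of the applied dose over a 12 hour wear time. At least 95% (665 mg) of lidocaine is expected to remain", with 700 mg of lidocaine per patch. The Mylan patch is said to deliver 11 ± 4% "of the applied dose over a 12 hour wear time. At least 82% (115 mg) of lidocaine is expected to remain", with 140 mg per patch.

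**The concern.** A reader who matches 10.3 to 10.4 will attach the 80% to the treatment test at 0.05, because that is the only test there is and because 10.3 speaks of rejecting a null and establishing significance. A 5% difference is very small against 22% within-subject variability in 24 subjects, so 80% power to detect it is implausible.

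If the true patch ratio is near 0.95, the planned test will be non-significant about 88% of the time, and 10.3 invites the reader to take that as the result of an 80%-powered comparison. The study is meant to inform regulatory guidance (sections 2.1 and 2.2), so the misreading matters. The harm is confined to small differences.

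Separately, the rationale for n=24 says nothing about how precisely absolute bioavailability will be estimated.

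**Working it through.** **Inputs.** n=24 completers, 12 per sequence (sections 5 and 7.3). Within-subject CV 22%, ratio 0.95 or 1.05, alpha 0.05 (section 10.3). Test of treatment at 0.05 on the log scale (section 10.4), taken as two-sided. The two treatments are read as the two patches, which fits the test and reference formulations of 10.3 and the two sequences. Within-subject SD on the log scale: σ = √ln(1+0.22²) = 0.2174. Standard error of the log ratio: σ√(2/24) = 0.0628. Degrees of freedom: 24−2 = 22.

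**Reproducing n=24.** Two one-sided tests, each at 0.05, with assumed limits 0.80-1.25 and true ratio 0.95:

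| n | σ=0.2174 | 0.22 used directly as σ |
|---|---|---|
| 20 | 76.2% | 75.2% |
| 22 | 80.4% | 79.5% |
| 24 | 83.8% | 83.0% |

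Under the second reading, 24 is exactly the smallest even n that reaches 80%. The stated inputs therefore fit an equivalence calculation, but only with limits that the plan does not contain.

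**Power of the planned difference test.** Noncentral t, critical value 2.074, both tails, n=24:

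- Ratio 0.95: noncentrality 0.0513/0.0628 = 0.817; power 0.1194 + 0.0030 = 12.2%.
- Ratio 1.05: noncentrality 0.0488/0.0628 = 0.777; power 0.1120 + 0.0034 = 11.5%.
- 80% power is reached at ratios 0.83 and 1.20.
- n for 80% power: 284 (ratio 0.95) or 314 (ratio 1.05).

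A simulation of 400,000 trials agreed.

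**Sensitivity to the reading.** At ratio 0.95, a CV of 18%, 26% or 30% gives 15.9%, 10.2% or 8.9%. At CV 22%, a one-sided test gives 18.6% to 19.7% across the two ratios. If the 22% is the SD of the within-subject difference, power is 18% to 20% two-sided and 28% to 30% one-sided. No variant approaches 80%.

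**Precision at n=24.**

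- Patch ratio of AUC or Cmax: 95% CI factor exp(±2.074 × 0.0628) = 0.88 to 1.14 times the estimate.
- Absolute bioavailability on the log scale, from within-subject variation alone (22% assumed for the IV arm too): also 0.88 to 1.14.
- Absolute bioavailability if the ± terms in 6.1 are between-subject SDs of a log-normal quantity (assumption). Lidoderm: CV 2/3, log SD 0.606, exp(±2.069 × 0.606/√24) = 0.77 to 1.29. Mylan: CV 4/11, log SD 0.352, giving 0.86 to 1.16.

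**The 5% against section 6 (secondary).** Nominal amounts per patch are 0.03 × 700 = 21.0 mg and 0.11 × 140 = 15.4 mg, a ratio of 0.73. There the difference test has 99.7% power and the assumed equivalence test about 0.1%. Taking the ± terms at face value, the amounts run from 7 to 35 mg and from 9.8 to 21 mg. These are amounts delivered and not Cmax, and section 2.3.1 gives one expected peak for a regimen used with both patches. A ratio near 0.95 is not excluded, so this is a tension and not a proven contradiction.

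**The case against.** The strongest reply is that 10.3 is an ordinary equivalence calculation, badly described. A statement that test and reference differ by 5% is odd as a difference to detect but natural as an equivalence input, and the resulting n fits. The 0.05 in 10.4 covers treatment, period and sequence together, which reads as routine reporting of model terms. It is not called the powered test and no decision hangs on it. A 90% interval could be computed from the planned mean differences and standard errors. On this view the defect is an unstated null and margin, 12% is the power of a test nobody meant to power, and the matter is a clarification. The two treatments in 10.4 are also unnamed, and in 10.2 similar wording could mean patch and IV.

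Much of this stands as an account of where 24 came from, and it is why 24 is not called an error. It does not rescue the text. Section 10.3 speaks of statistical significance, 10.1 sets an estimation objective, and no equivalence hypothesis or analysis appears anywhere. The ambiguity about treatments changes what the test means but not its power, which with these inputs is the same for any within-subject contrast of two treatments. The point that about 12% depends on one reading is fair, so the range is shown; it tops out at about 30%. The bioavailability intervals built on the ± terms in 6.1 do rest on undefined quantities and should be treated as illustrative.

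**Conclusion.** The concern holds and should be fixed. The 80% power is a property that the planned treatment test does not have: for a 5% difference its power is about 12%, against 80% only for ratios near 0.83 or 1.20. This rests on 22% being a within-subject CV, a two-sided test and 24 completers. The only calculation found that matches n=24 is an equivalence test under 80-125% limits, which are assumed here and belong to an analysis the plan never states.

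The consequence is limited to how small patch differences are read; a large difference, such as the nominal 0.73, would be detected almost surely. The missing precision statement for absolute bioavailability is a separate gap in the same paragraph.

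**What to change.** Keep n=24. In 10.3, delete the claims of 80% power, null rejection and a 5% difference, and state instead:

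1. At 22% within-subject CV, the 95% CI for the Mylan/Lidoderm ratio of AUC or Cmax is expected to run from 0.88 to 1.14 times the estimate.
2. The treatment test at 0.05 has about 80% power for ratios near 0.83 or 1.20.
3. The expected 95% CI width for each patch's absolute bioavailability, on the log scale of the AUC estimator in 10.2, with the source of the variance named.

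Name the two treatments in 10.4. If the authors did intend equivalence, they should instead state the null, the margins and the 90% CI in 10.1 and 10.4, reconcile the assumed ratio with section 6.1, and report the resulting power.

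The first route costs one reworded paragraph, with no added subjects, visits or samples. The price is a less favourable claim, because the plan can no longer say it has 80% power for a 5% difference.
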